9.2 Follow-up Visit 1 (2nd study visit)

The first follow-up visit will be scheduled 2 weeks (± 1 week) after the first study visit.

During this visit, fittings of the SONNET and the SONNET 2 or will be confirmed prior to any study test and only adjusted if needed.

9.2.1 Testing with the current audio processor (SONNET):

- Speech test in noise (S0N0)

9.2.2 Testing with the SONNET 2:

- User satisfaction and sound quality rating via questionnaires
- MAESTRO Export of all SONNET 2 configurations including the data logging information
- Speech test in noise (S0N0)
 - ❖ Set-up as an OPUS 2
 - ❖ Set-up as an SONNET (without new front-end features)
 - ❖ Setting 1: ASC off, mild WNR, mild NR, mild TR
 - ❖ Setting 2: ASC off, mild WNR, strong NR, strong TR
 - ❖ Setting 3: ASC mild, mild WNR, auto NR, auto TR
 - ❖ Setting 4: ASC strong, strong WNR, auto NR, auto TR
- Speech test in noise (S0N0T0)
 - ❖ Set-up as an SONNET (without new front-end features)
 - ❖ Setting 1: ASC off, mild WNR, mild NR, mild TR
 - ❖ Setting 2: ASC off, mild WNR, strong NR, strong TR
- Reset the data logging in all configurations
- Send subject home with two SONNET 2 configurations (randomized across subjects) with data logging set to zero

9.3 Follow-up Visit 2 (3rd study visit)

The first follow-up visit will be scheduled 2 weeks (± 1 week) after the second study visit.

During this visit, fittings of the SONNET and the SONNET 2 or will be confirmed prior to any study test and only adjusted if needed.

9.3.1 Testing with the current audio processor (SONNET):

- Speech test in noise (S0, $\pm N45$, $\pm N135$)

9.3.2 Testing with the SONNET 2:

- User satisfaction and sound quality rating via questionnaires
- MAESTRO Export of all SONNET 2 configurations including the data logging information
- Speech test in noise (S0, $\pm N45$, $\pm N135$)
 - ❖ Set-up as an OPUS 2
 - ❖ Set-up as an SONNET (without new front-end features)
 - ❖ Configuration 1: ASC off, mild WNR, mild NR, mild TR
 - ❖ Configuration 2: ASC off, mild WNR, strong NR, strong TR
 - ❖ Configuration 3: ASC mild, mild WNR, auto NR, auto TR
 - ❖ Configuration 4: ASC strong, strong WNR, auto NR, auto TR
- Reset the data logging in all configurations
- Send subject home with two SONNET 2 configurations (randomised across subjects) with data logging set to zero

9.4 Follow-up Visit 3 (4th study visit)

The first follow-up visit will be scheduled 2 weeks (± 1 week) after the third study visit.

During this visit, fittings of the SONNET 2 will be confirmed prior to any study test and only adjusted if needed.

9.4.1 Testing with the SONNET 2:

- User satisfaction and sound quality rating via questionnaires
- MAESTRO Export of all SONNET 2 configurations including the data logging information
- Subjective sound quality ratings (S0N0T0) and the ACALES test in noise (S0N0) to evaluate the NR and TR for the following audio processor configurations
 - ❖ Set-up as an OPUS 2
 - ❖ Set-up as an SONNET (without new front-end features)
 - ❖ Configuration1: ASC off, mild WNR, mild NR, mild TR
 - ❖ Configuration 2: ASC off, mild WNR, strong NR, strong TR
- Reset the data logging in all configurations

- Send subject home with two SONNET 2 configurations (randomised across subjects) with data logging set to zero

9.5 Follow-up Visit 4 (5th study visit)

The first follow-up visit will be scheduled 2 weeks (± 1 week) after the fourth study visit.

During this visit, fittings of the SONNET 2 will be confirmed prior to any study test and only adjusted if needed.

9.5.1 Testing with the SONNET 2:

- User satisfaction and sound quality rating via questionnaires
- MAESTRO Export of all SONNET 2 configurations including the data logging information
- Subjective sound quality ratings (S0, $\pm N45$, $\pm N135$, T135 ipsilateral to the CI) and the ACALES test in noise (S0, $\pm N45$, $\pm N135$) to evaluate the NR and TR for the following audio processor configurations
 - ❖ Set-up as an OPUS 2
 - ❖ Set-up as an SONNET (without new front-end features)
 - ❖ Configuration 1: ASC off, mild WNR, mild NR, mild TR
 - ❖ Configuration 2: ASC off, mild WNR, strong NR, strong TR

9.6 Early Termination Visit

If a subject withdraws from the study, he or she can do so during a regular study visit. In this case, the subject gives back the SONNET 2 audio processor and the centre gives him/her back their own SONNET audio processor and ensures that fitting is appropriate. In case a subject withdraws from the study outside of a study visits, an early termination visit shall be scheduled to follow-up on any potential open issues and document reasons for the withdrawal. During this visit, the subject gives back the SONNET 2 audio processor and the centre gives him/her back their own SONNET audio processor and ensures that fitting is appropriate. In any case, the case report form "Early Withdrawal Form" will be completed.

9.7 Unscheduled Visit(s)

In the case of any unexpected events, subjects may present at the clinic in-between regular study visits. During unscheduled visits the CRF "Unscheduled visit" shall be completed.

10 EQUIPMENT AND TEST METHODOLOGIES

10.1 Equipment

10.1.1 MAESTRO Software

Within the MED-EL Cochlear Implant System, MAESTRO 8 is used to program system components in order to achieve an optimal benefit for each individual implant patient. MAESTRO 8 consists of the software application, the installation program, and the accompanying labelling (instructions for use and CD labelling). Like its predecessor MAESTRO 7, MAESTRO 8 is designed and developed via the Microsoft .NET Framework and intended to be run on a personal computer that has a Microsoft Windows™ operating system installed. To communicate with implants and audio processors MAESTRO 8 uses the MAX Programming Interface which is connected via the standard USB 2.0 interface to the personal computer on which the software is running.

With MAESTRO 8 it is possible to program the new SONNET 2 audio processor and the new front-end processing features can be activated. The SONNET 2 audio processor comes equipped with various new ASM features (e.g. noise reduction, transient reduction, and automatic scene classification).

As MAESTRO 8 is a component of the MED-EL Cochlear Implant System, all indications stated for the MED-EL Cochlear Implant System are applicable.

MAESTRO 8 is intended to be used:

- In a clinical or office environment by persons adequately skilled and trained to perform all intended tasks
- With patients who received one of the intended MED-EL cochlear implants
- Installed on a Personal Computer running a version of the supported Microsoft Windows operating system
- All tasks which can be performed are described in the MAESTRO 8 manual.

10.2 Tests/Material

10.2.1 Impedance Field Telemetry (IFT)

A telemetry recording will be performed according to the procedures explained in the MED-EL Fitting Guide. The impedance field telemetry (IFT) recording ensures the proper function of the implant and measures impedances on all electrodes as well as the ground path.

These data form the basis of every clinical map and are necessary to interpret differences between fitting maps.

10.2.2 **Speech testing in quiet**

The Freiburg Monosyllabic test is an open-set monosyllabic word test and is widely used to test adults in German-speaking countries (K.-H. Hahlbrock & Zöllner, 1970; K. H. Hahlbrock, 1970). It consists in total of 20 lists with 20 words each. Each patient shall perform a training starting the actual testing. The results scored in this training session will not be analysed. The test lists will be allocated according to a randomization procedure. The analysis evaluates the number of correctly repeated words in % correct at a fixed presentation level. Speech is presented at 65dB SPL. The test shall be performed in quiet.

10.2.3 **Speech testing in noise**

In this study speech audiometry in noise will be performed using Oldenburger matrix sentence tests (Wagener, Brand, & Kollmeier, 1999a, 1999b; Wagener, Kühnel, & Kollmeier, 1999).

Oldenburger matrix sentence tests are available as measurement modules of the Oldenburger Measurement Application (OMA) (Hörtech GmbH). Matrix sentence tests will be used in the study, due to the sensitivity and applicability in a two-language study. Speech audiometry with the Oldenburger matrix sentence test using speech test material in the national language of the study site.

The test is used to assess the 50% speech-recognition threshold (SRT50 in dB SNR), which is a measure of the level difference at which speech can be identified at half the time in presence of simultaneous masking noise.

The sentences of matrix tests all are composed with the same structure. Test lists with 20 or 30 items are generated from several such sentences. The words are taken in a seemingly random fashion from an inventory (a matrix) of 50 words (10 words per category).

10.2.4 **Subjective user ratings**

10.2.4.1 **Audio Processor Satisfaction Questionnaire (APSQ)**

The APSQ is a validated general questionnaire which is designed to assess the handling of MED-EL devices. It assesses the wearing comfort, sound quality, and other device-specific factors related to the audio processor. The APSQ will be filled out by the patients at the first visit for the OPUS 2 before they get the SONNET and at the third visit for the SONNET. A copy of the completed questionnaire shall be sent to the study monitor. A copy of the completed questionnaire shall be sent to the study monitor.

10.2.4.2 ***Hearing Implant Sound Quality Index 19 (HISQUI19)***

The Hearing Implant Sound Quality Index 19 (HISQUI19) is a self-administered questionnaire to quantify the individual perceived sound quality of hearing implanted patients in daily life (Amann & Anderson, 2014). The questionnaire consists of 19 seven-level Likert items ranging from “always (99%)” to “never (1%)”. Added percentage values shall support the answering. Eight additional items assess the current sound sensation of the patients implanted. The HISQUI19 takes about 15 minutes to complete. It will be filled out by the patients at the first visit for the OPUS 2 before they get the SONNET and at the third visit (final visit) for the SONNET. Documentation of the results shall be recorded in the appropriate sections of the case report forms. A copy of the completed questionnaire shall be sent to the study monitor.

10.2.4.3 ***SSQ12 (Speech Spatial Qualities) in German***

The speech, spatial, and qualities of hearing (SSQ) questionnaire is used in its shorter 12-question version (Noble, Jensen, Naylor, Bhullar, & Akeroyd, 2013). The short version of the SSQ questionnaire provides similar results to the full version comprising 49 questions. A conversion formula between the abbreviated and full versions has been provided previously (Noble et al., 2013). The SSQ questionnaire is a sensitive and specific measure to assess the impact of hearing loss on speech perception, sound localization, and QoL. The SSQ12 covers:

- Hearing speech in a variety of competing contexts;
- The directional, distance and movement components of spatial hearing
- Segregation of sounds and attending to simultaneous speech streams;
- Ease of listening;
- The naturalness, clarity and identifiability of different speakers, different musical pieces and instruments, and different everyday sounds.

SSQ12 has a scale from 0 (not at all) to 10 (perfectly) and allows to rate every answer everywhere inside that scoring frame.

The SSQ12 will be filled out by the patients at the first visit for the OPUS 2 before they get the SONNET and at the third visit for the SONNET. A copy of the completed questionnaire shall be sent to the study monitor.

10.2.4.4 ***SONNET 2 questionnaire***

A study specific questionnaire was developed to investigate how the four new SONNET 2 fitting configuration compare to the previous SONNET settings. The questionnaire covers different everyday situations (e.g. conversations in a cocktail party setting, speech different background noise situations, music etc.). The subjects are asked to state which fitting

configuration is preferred and give a reason why. Additionally, there are blank spaces which each subject can state situations which are important to each individual, state their preferred fitting and also tick why a particular fitting was preferred.

10.2.4.5 ***Subjective sound quality rating***

In addition to questionnaires, subjects are asked to subjectively rate the sound quality of the different fitting configuration. The subjective sound quality of the different SONNET 2 configurations will be assessed on a visual analogue scale (VAS) for a range of signals comprising different samples of speech, music, and background noises. The subject will have to rate the perceived quality on different scales, compared to a reference condition.

10.2.4.6 ***ACALES Test***

To evaluate the listening effort induced by different configurations, the ACALES test will be performed (Krueger & Schulte, 2017). In this test, the subject will listen to speech in noise and rate the subjectively perceived listening effort on a scale from “effortless” to “extremely effortful”. Depending on the rating of the subject, the level of the speaker will be varied adaptively while the noise level is kept constant. This test will be performed in different fitting configurations.

11 STUDY PROCEDURES

11.1 Demographics and Medical Data

The Investigator will record age and gender of the subject. Demographic data will be recorded in the appropriate section of the CRF at the screening visit and confirmed at every subsequent visit by the Investigator, as applicable

11.2 Medical History

Generally, the Investigator will record the medication history according to clinical standards in order to evaluate whether the subjects fulfils indication and inclusion criteria and does not fulfil any contraindications or exclusion criteria for CI surgery in general and for the study participation in particular. Results from the examination will be reported in the respective CRFs as applicable.

11.3 Medication

The Investigator will record the medication history according to clinical standards in order to evaluate whether the subject fulfils indication and inclusion criteria of the study. Results from the examination will be reported in the respective CRFs as applicable.

11.4 Compliance with the Selection Criteria

During the screening visit the Investigator thoroughly evaluates whether a subject meets the selection criteria and can be enrolled into the study. This does not imply that the subject needs to perform any kind of study specific testing. In case a subject meets the criteria and is willing to participate, the Investigator will explain all the involved procedures, risks and benefits of the clinical investigation understandably and will answer all upcoming questions. The subject will read the ICF, sign and date it. A written copy of the ICF will be given to the subject and can be taken home. The compliance of the subject with the study inclusion and exclusion criteria will be documented in the appropriate section of the CRF at each visit by the Investigator.

11.5 Special Tests/Procedures

11.5.1 Fitting procedure

Appropriate fitting for the subject's SONNET will be confirmed according to clinical routine and then receive the upgrade to the SONNET 2. The SONNET 2 will be fitted based on the most current clinical map of the subject. Adjustments to the fitting map imported can be made if deemed necessary according to the clinical routine procedures. Adjustments to the fitting maps across the study visits are possible if deemed necessary according to the clinical routine procedures. Clinical maps will be recorded as part of the study.

11.5.1.1 *Telemetry (IFT) recording*

Perform a routine telemetry recording as explained in the MAESTRO user guide. There are no parameters to be adjusted. Save the telemetry recording in MAESTRO and rename it according to the following scheme: "*SubjectIDIFT_visit name*".

11.5.1.2 *MCL and THR recording*

The standard fitting procedure as implemented at the study centre as per clinical routine will be used to determine MCL and THR levels. Briefly, THR and MCL levels are measured using verbal feedback from the patient. THR levels may be obtained using an ascending presentation, followed by a standard bracketing procedure. MCLs are obtained through a method referred to as loudness scaling. The level of current is gradually increased, while the patient reports on the level of loudness and comfort. Ideally, MCL levels should also be balanced across the electrode array. Loudness balancing requires comparison on at least two electrodes at a time until all MCLs are perceived as equally loud. After adjusting the parameters according to the subject's needs, save the THR and MCL recording in MAESTRO and rename it according to the following scheme: "*SubjectIDTHRs_visit name*" and "*SubjectIDMCLs_visit name*".

11.5.2 Speech testing

11.5.2.1 *Freiburg Monosyllables*

The Freiburg Monosyllables in quiet will be implemented according to the routine testing approach at the study centre. The results are recorded and expressed in % correct and reported in the CRFs.

11.5.2.2 **OLSA**

The Oldenburger Matrix Sentence Test will be performed according to the specification in the case report form (e.g. order of configuration etc.). Prior to the test lists, a training round will be performed at each visit. Noise level will be fixed to 60 dB SPL and the speech level will be adaptive.

The OLSA will be performed in different set-ups (also see Figure 1):

- S0N0

Speech and noise signal are both presented from the front of the subject (0° angle).

- S0N0T0

Speech, noise and transient noise are presented from the front of the subject (0° angle).

- S0, $\pm 45^\circ$, $\pm 135^\circ$

Speech is presented from the loudspeaker in front of the subject (0° angle). Stationary noise presented from +45° and -45° angle and +135° and -135° angle.

[figure not shown]

Figure 1 Loudspeaker set-up

11.5.3 **Subjective user ratings**

11.5.3.1 **Audio Processor Satisfaction Questionnaire (APSQ)**

The APSQ will be completed by the subject. An instruction is given in the questionnaire document. These data are considered source data.

11.5.3.2 ***Hearing Implant Sound Quality Index 19 (HISQUI19)***

The HISQUI will be completed by the subject. An instruction is given in the questionnaire document. These data are considered source data.

11.5.3.3 ***SSQ12 (Speech Spatial Qualities) in German***

The SSQ12 will be completed by the subject. An instruction is given in the questionnaire document. These data are considered source data.

11.5.3.4 ***SONNET 2 questionnaire***

The SONNET 2 Questionnaire will be completed by the subject. An instruction is given in the questionnaire document. These data are considered source data.

11.5.3.5 ***Subjective rating***

11.5.3.6 ***ACALES Test***

To evaluate the listening effort induced by different configurations, the ACALES test will be performed. In this test, the subject will listen different sound files and rate the subjectively perceived listening effort on a scale from “effortless” to “extremely effortful”. Depending on the rating of the subject, the level of the signal will be varied adaptively while the noise level is kept constant,

The ACALES will be performed in different set-ups (also see Figure 1):

- S0N0

Speech and noise are both presented from one loudspeaker being in front of the subject (0° angle).

S0, $\pm N45$, $\pm N135$ \pm Speech is presented from the loudspeaker in front of the subject (0°angle). Stationary noise is presented from +45° and -45° angle and +135° and -135° angle.

11.5.3.7 ***Subjective sound quality rating***

[figure not shown]
The subjective sound quality of the different configurations will be assessed on a visual analogue scale (VAS) for a range of signals. The subject will have to rate the perceived quality on different scales, compared to the reference condition (Set-up as an SONNET (without new front-end features).

- Overall quality: Scale ranging from ‘Much better’ to ‘Much worse’

- Listening effort: Scale ranging from 'Much less effortful' to 'Much more effortful'
- Listening comfort: Scale ranging from 'Much more comfortable' to 'Much less comfortable'
- Annoyance of background signal: Scale ranging from 'Much less annoying' to 'Much more annoying'
- Acceptability of the program (no reference necessary): 'Not acceptable' to 'Very acceptable'

[figure not shown]
[figure not shown]
[figure not shown]
11.5.4 Scientific data export

After each take home period, the data of all configurations is exported and saved using the scientific export of MEASTRO. This data contains, among others, the logging data information (e.g., the processor usage, exposure time in the different audio environments, etc.) and enables to draw a relation between subjective ratings (questionnaires) and exposure to various audio environments during the take home periods.

11.6 Randomization

The order of the audio processor testing (see Section 9 for details) will be randomised for each subject and study visit. Additionally, it will be randomised, which audio processor configurations will be taken home after a particular visit. These randomizations will be performed to avoid any sequence-effects (e.g. training effect, fatigue effect). The particular fitting configuration and the order of the test procedures is verbally stated in the respective CRFs for each subject and each study visit. Hence, no de-randomisation procedure is necessary.

Confidential

CIP Version: 1.2

Template version: 3.0

Clinical Investigation Plan
FEP3, [REDACTED]
09 May 2019

Page 50 of 75

Confidential

CIP Version: 1.2

Template version: 3.0

Clinical Investigation Plan
FEP3, [REDACTED]
09 May 2019

Page 51 of 75

Confidential

[figure not shown]
CIP Version: 1.2

Template version: 3.0

Clinical Investigation Plan
FEP3, [REDACTED]
09 May 2019

Page 52 of 75

Confidential

CIP Version: 1.2

Template version: 3.0

Clinical Investigation Plan
FEP3, [REDACTED]

09 May 2019

Page 53 of 75

Confidential

CIP Version: 1.2

Template version: 3.0

Clinical Investigation Plan
FEP3, [REDACTED]
09 May 2019

Page 54 of 75

Confidential

CIP Version: 1.2

Template version: 3.0

Clinical Investigation Plan
FEP3, [REDACTED]
09 May 2019

Page 55 of 75

Confidential

[figure not shown]
CIP Version: 1.2

Template version: 3.0

Clinical Investigation Plan
FEP3, [REDACTED]
09 May 2019

Page 56 of 75

Confidential

CIP Version: 1.2

Template version: 3.0

Clinical Investigation Plan
FEP3, [REDACTED]
09 May 2019

Page 58 of 75

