7.3 Sample Size Calculation

The primary objective of this study is to show non-inferiority of SONNET2 in a OLSA in noise speech test (S0N0) compared to the SONNET. The margin of non-inferiority is set to 2 dB SNR (Hey et al., 2014; Nogueira et al., 2016).

Comparable data of the final report "Performance of Cochlear Implant Patients with Microphone Directionality and Wind Noise Reduction with the "SONNET" of the OLSA in noise speech test (S0N0) were used as basis for the sample size calculation (Hagen et al., In submission):

OPUS2	mean: 0.589 dB;	± SD: 1.586 dB vs.
SONNET natural-MILD	mean: -0.088 dB;	± SD: 1.463 dB

The sample size was estimated using the formula on noninferiority (Chow, Shao, & Wang, 2008):

$$N = (1 + \frac{1}{r})(\sigma \frac{Z_{crit} + Z_{pwr}}{(\mu_A - \mu_B) - \Delta})^2$$

Assuming a non-inferiority margin of 2 dB (Δ), with an alpha-level of 0.025 (noninferiority, one-sided) and a power of 90%, a minimum sample size of 13 subjects was calculated (Z_{crit} is the normal quantile for the 0.025 alpha level, and Z_{pwr} is the normal quantile for the 90%

power). To allow for possible dropouts (approximately 20%) and to provide additional safety and efficacy data, a maximum of 30 subjects will be included in this study.

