7.5 Randomization and Blinding

The order of the audio processor testing will be randomised for each subject and study visit. Additionally, it will be randomised which audio processor configurations will be taken home after a particular visit. These randomizations will be performed to avoid any sequence-effects (e.g. training effect, fatigue effect). The particular fitting configuration and the order of the test procedures is verbally stated in the respective CRFs for each subject and each study visit.

Details on randomization can be found in the Data Management Plan (DMP).

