11.2.2 Secondary Objectives

The secondary objectives of this study are of an explorative nature and provide additional evidence on the performance of SONNET 2-specific front-end features. The performance of the SONNET 2 will be assessed with different combinations of frontend processing features under different environmental test conditions using the following tests:

- Speech performance
 - ◆ Freiburg Monosyllabic test in quiet; speech presented from the front
 - ◆ Oldenburg Sentence Test in noise in the set-ups:
 - ⇒ S0N0
 - ⇒ S0N0T0
 - ⇒ S0, ±N45, ± N135
- Quality of hearing in real life
 - ◆ HISQUI19
 - ◆ SSQ12
- Device handling

- ◆ Data Logging
- ◆ APSQ
- Subjective Rating
 - ◆ ACALES
 - ◆ Subjective Sound Quality Rating
 - ◆ Product Specific Questionnaire

The Kolmogorov-Smirnov test, the Shapiro-Wilk test and a graphical examination will be conducted in a first step to check the data distribution of the secondary endpoints. Based on the data parametric and/or non-parametric tests such as the Paired sample t-test or the Wilcoxon signed-rank test will be applied.

12 Data Handling

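### Test order is randomised and recorded but no planned analysis uses it, which costs precision in the seven-condition speech tests if order effects exist

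*Protocol*

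**What the plan says.** SAP section 7.5 states: "The order of the audio processor testing will be randomised for each subject and study visit". Protocol section 11.6 has the same rule and gives its purpose: "These randomizations will be performed to avoid any sequence-effects (e.g. training effect, fatigue effect". Both sections add that the order appears in the CRF for each subject and visit, so it will be available to the analyst. SAP section 7.5 leaves the details of the randomisation to the Data Management Plan.

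The number of conditions per session differs by test (protocol sections 9.1 to 9.5):
- Seven conditions (the subject's own SONNET and six SONNET 2 configurations): Freiburg in quiet at visit 1, OLSA S0N0 at visit 2, and OLSA with noise at ±45° and ±135° at visit 3.
- Three SONNET 2 configurations: OLSA S0N0T0.
- Four SONNET 2 configurations: ACALES and the sound quality rating.

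None of the analysis sections has a term for order or position. Protocol sections 15.1.1 and 15.1.2 name Student's t-test or the Wilcoxon signed-rank test. SAP section 11.2.1 plans a mean difference with a 95% CI for the primary contrast. For the secondary endpoints SAP section 11.2.2 says: "Based on the data parametric and/or non-parametric tests such as the Paired sample t-test or the Wilcoxon signed-rank test will be applied".

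**The concern.** The plan expects performance to drift within a session, randomises to guard against it, records the order, and then leaves it out of the analysis. Randomisation stops drift from favouring one configuration on average. It does not remove the drift from the data. If two configurations sit at different positions in a subject's session, that subject's difference contains the drift between the positions. Across subjects this adds to the SD of the paired difference and widens the interval.

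At stake are the comparisons across all processors and settings, which are the secondary objectives. They may rest on as few as 13 subjects, and the contrasts of interest may be well under 1 dB.

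**Working it through.** **The plan's own figure.** Protocol section 7.3 gives planning SDs of 1.586 and 1.463 dB, a 2 dB margin, one-sided alpha 0.025 and 90% power. The pooled SD is √((1.586² + 1.463²)/2) = 1.526 dB. With r = 1 and a true difference of 0 (both assumed), N = 2 × (1.526 × 3.2415 / 2)² = 12.23, which rounds up to the stated result: "a minimum sample size of 13 subjects was calculated". The upper limit is 30, or 30 × 0.8 = 24 completers at the plan's 20% dropout. A position term changes none of this.

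**Inputs the documents do not give.** Within-subject SD (sw): 1.0 dB assumed, with 0.75 to 1.5 dB as the range for power. Linear drift b: 0 to 0.3 dB per position assumed, which over six steps is 0 to 1.8 dB from first to last test. Order: unrestricted permutation assumed.

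**Order variance in one paired difference.** For k conditions in random order, the variance of the position gap is k(k+1)/6.
- k = 7: 9.33, SD 3.06
- k = 4: 3.33, SD 1.83
- k = 3: 2.00, SD 1.41

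The variance of the difference is therefore 2sw² + b² × k(k+1)/6. With a drift of 1 dB over the session and k = 7, the added variance is (1/6)² × 9.33 = 0.259 dB². Against 2sw² = 2.0 at sw = 1.0, this is an inflation of 1.13.

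**Validity.** In simulation with drift up to 2 dB over the session, the paired t-test had bias of at most about 0.02 dB, type I error of 4 to 6% and coverage of 94 to 96%. Chance order imbalance in a mean contrast at 1 dB drift has SD √(0.259/13) = 0.14 dB at 13 subjects and √(0.259/30) = 0.09 dB at 30. The paired interval already includes it.

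**Gain from a joint model** (subject, configuration and position, common error, seven conditions, sw = 1.0), as the reduction in 95% CI width against the paired t:

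| Drift per position | n = 13 | n = 30 |
|---|---|---|
| 0 dB | about 2% | about 1% |
| 0.1 dB | 5% | 4% |
| 0.2 dB | 11% | 9% |
| 0.3 dB | 19% | 18% |

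For S0N0T0, with three conditions, the ratio of widths ran only from 1.006 to 0.963 over the same drifts.

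**What happens if variances differ.** With no drift, suppose the compared pair has sw 0.8 dB and the other conditions 1.2 dB. The common-error interval is then 33 to 36% wider than the paired one. If the pair has 1.4 dB and the rest 1.0 dB, coverage falls to about 88 to 90%.

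**A form with pair-specific error.** Regress the within-subject difference on the difference in position and report the intercept. With no drift this is about 5% wider than the paired t at 13 subjects and 2% wider at 30. Removing the order variance multiplies the width by √(2/(2 + 9.33b²)), which is 0.977, 0.918 and 0.839 at 0.1, 0.2 and 0.3 dB. The net ratio at 13 subjects is about 1.05 times these: 1.03, 0.96 and 0.88. At 30 subjects it is about 1.02 times these: 1.00, 0.94 and 0.86.

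**Primary contrast.** With a true difference of 0 and 24 subjects, non-inferiority power is at least 0.978 for sw of 0.75 to 1.5 dB and drift up to 2 dB over the session. At 13 subjects and sw = 1.0 it is 0.997, 0.992 and 0.966 at drifts of 0, 1 and 2 dB. At sw = 1.5 it is 0.877, 0.858 and 0.803.

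**The case against.** The strongest reply is that nothing is wrong. Randomising order is a recognised control, the paired analysis under it is valid, the secondary endpoints are declared exploratory, and the wording of SAP section 11.2.2 leaves other methods open. Validity stands: this is a matter of efficiency. The open wording is a weaker defence, because SAP section 3 says the document exists to prevent post hoc choices.

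The reply also notes that the size of the gain is assumed. Protocol section 11.5.2.2 puts a training round before the OLSA lists at each visit, and training and fatigue pull in opposite directions, so a steady one-way drift is a favourable case for adjustment. The order may also be balanced in the Data Management Plan. These points stand, and they are why the gain is given as a range starting at no drift.

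A reader might infer more than the documents support:
- **That the contrasts are biased.** They are not.
- **That every contrast is affected.** S0N0T0 gains almost nothing. HISQUI19, SSQ12 and APSQ are not tests run in a within-session order. The SAP primary is a mean difference with a CI.
- **That a joint model can never do worse.** That depends on equal variances. Protocol Table 2 mixes fixed and automatic beamforming, with noise reduction from absent to strong, so equal variances cannot be taken for granted.

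**Conclusion.** The point holds as a conditional loss of precision, confined to the speech tests with seven conditions in one session. Its size rests on an assumed drift, an assumed within-subject SD, unrestricted random order and equal variances. Under these it runs from 1 or 2% of CI width with no drift to 18 or 19% at 0.3 dB per position. An analysis that keeps pair-specific error gains less, and pays a small price if there is no drift.

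The dB figures apply to the OLSA. For Freiburg the same reasoning applies with drift measured relative to the within-subject SD, but a 20-word list moves in 5-point steps on a bounded scale, so a normal model is an approximation. Adding a position term does not settle the choice between t-test and Wilcoxon.

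The primary non-inferiority conclusion is little affected at planned enrolment, and the minimum of 13 does not change. This is a cheap improvement, not a correction of an error.

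**What to change.** In SAP section 11.2.2, for each of the three seven-condition speech set-ups, pre-specify a linear mixed model with fixed effects for configuration and test position and a random subject effect. Let the residual variance differ by configuration, or use an unstructured or robust covariance with small-sample degrees of freedom. Report configuration contrasts with 95% CIs. The simpler alternative is the regression of the paired difference on the position difference, reporting the intercept. Do not use one pooled error for all configurations.

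Keep the planned paired test as a sensitivity analysis. For the primary contrast in SAP section 11.2.1, use the position-adjusted estimate as supportive only. State in the SAP whether the order is balanced across subjects or freely permuted.

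The cost is SAP wording and a standard model run, with no new data, visits or subjects, because the order is already in the CRF. The downside is a few degrees of freedom: for the regression form, about 5% in width at 13 subjects and 2% at 30 if there is no order effect.
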